1 LIST OF ABBREVIATIONS

ACL	Anterior Cruciate Ligament
ADE	Adverse Device Effect
AE	Adverse Event
ALT/SGPT	Alamine Transaminase/Serum Glutamic Pyruvic Transaminase
ANOVA	Analysis of Variance
AP	Anterior Posterior
AR	Adverse Reaction
AST/SGOT	Aspartate Aminotransferase/Serum Glutamic Oxaloacetic Transaminase
BMI	Body Mass Index
CFR	Code of Federal Regulations
cm	Centimeters
CRO	Contract Research Organization
CTM	Clinical Trial Material
CV	Curriculum Vitae
D/C	Discontinued
DMP	Data Management Plan
eCRF	electronic Case Report Form
EDC	Electronic Data Capture
EQ-5D	EuroQoL 5 Dimension
EQ VAS	EuroQoL Visual Analog Scale
EULAR	European League Against Rheumatism
FDA	Food and Drug Administration
g, mg, kg	gram, milligram, kilogram
GCP	Good Clinical Practices
GEE	Generalized Estimating Equations
h	hour(s)
HA	Hyaluronan / Sodium Hyaluronate / Hyaluronic Acid
HIPAA	Health Insurance Portability and Accountability Act
IA	Intraarticular
ICF	Informed Consent Form
ICH	International Conference on Harmonization
ID	Identification
IDMC	Independent Data Monitoring Committee
IEC	Independent Ethics Committee
IFU	Instructions for Use
IND	Investigational New Drug
ISO	International Organization for Standardization
ITT	Intent-to-Treat
K-L	Kellgren-Lawrence classification
MedDRA	Medical Dictionary for Regulatory Activities
mL, mm, m	milliliter, millimeter, meter
NSAIDs	Non-steroidal anti-inflammatory drug
OA	Osteoarthritis
OARSI	Osteoarthritis Research Society International
OMERACT	Outcomes Measures for Rheumatic Arthritis Clinical Trials
PA	Posterior Anterior
PE	Physical Exam
PI	Principal Investigator
PP	Per Protocol
RBC	Red Blood Cell

ROM	Range of Motion
SADE	Serious Adverse Device Effect
SAE	Serious Adverse Event
SAR	Serious Adverse Reaction
SAP	Statistical Analysis Plan
SOP	Standard Operating Procedure
SUSAR	Suspected Unexpected Serious Adverse Reaction
TEAE	Treatment Emergent Adverse Events
TH	triamcinolone hexacetonide
UADE	Unanticipated Adverse Device Effect
UK	United Kingdom
US	United States
VAS	Visual Analog Scale
WBC	White Blood Cell
WOMAC	Western Ontario and McMaster Universities Osteoarthritis Index

2 DEFINITIONS

Baseline: The assessments performed prior to the study injection after the Screening Visit.

Blinded Evaluator: The Blinded Evaluator will be a physician, research nurse, registered physiotherapist or physician assistant trained by the PI to perform the assessments outlined in the protocol. The Blinded Evaluator will complete the physical evaluation of both knees, range of motion (ROM) assessment of both knees, and the Evaluator Global Assessment.

End of Study: End of study is defined as the last subject's last visit.

Enrolled: A subject who has signed the informed consent form (ICF) is enrolled.

Index Knee: The knee that meets the eligibility criteria for treatment. The index knee may also be termed the "study knee". In subjects with bilateral knee Osteoarthritis (OA), where both knees meet eligibility criteria, the more symptomatic knee is the index knee.

Ethics Committee (EC): EC refers to an independent body (e.g. Research Ethics Boards, Independent Ethics Committees) whose responsibility is to ensure the protection of rights, safety and well-being of human subjects involved in a trial. Committees with these responsibilities will be referred to in this document as Ethics Committees.

Rescue Medication: Acetaminophen/paracetamol will be distributed as the rescue medication. It is the only medication that should be taken for knee pain during the entire study. Rescue medication will be discontinued at least 48 hours prior to Baseline and all follow-up visits.

Treating Physician: The Treating Physician will most often be the Principal Investigator (PI). He/she will administer the Cingal®, Monovisc® or steroid injection but will not participate in the efficacy evaluation.

Treatment Failure: A subject who undergoes a procedure or uses a medication (other than the rescue medication) for the treatment of OA in the index knee at any time after the study injection through the 39 week visit.

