7.3 Exploratory Endpoints

Any comparisons between groups (Cingal, Monovisc, TH), within groups and / or time points (from baseline through to 39 weeks) not described in the primary or secondary endpoints may be presented in the exploratory endpoints including:

[figure not shown]
- EuroQol (EQ-5D)
- WOMAC Pain Score (100mm VAS)
- OMERACT-OARSI
- Total WOMAC
- WOMAC Stiffness Score
- WOMAC Physical Function
- Patient Global Assessment
- Evaluator Global Assessment
- Range of Motion
- Rescue Medication Usage
- Number of Treatment Failures due to Additional Procedure or Use of Disallowed Medication

7.4 Safety Endpoint:

The incidence, timing, severity, and relationship to treatment of all Adverse Events (AE) will be collected and coded using Medical Dictionary for Regulatory Activities (MedDRA). Local injection site and non-local events will be recorded separately.

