9 ELIGIBILITY

9.1 Enrollment Criteria

9.1.1 Inclusion Criteria

1. Only subjects that were enrolled and met the inclusion criteria for the Cingal 16-02 trial and signed the informed consent are eligible for Cingal 17-02.
2. Subject is able to understand and comply with the requirements of Cingal 17-02 and voluntarily provides consent.

Patients will not be rescreened at enrollment to Cingal 17-02 as these patients were enrolled and met the inclusion / exclusion criteria for the Cingal 16-02 clinical trial. All patients enrolled in the Cingal 16-02 trial will be eligible to participate in Cingal 17-02.

For reference only, the inclusion criteria used in Cingal 16-02 were:

1. Subject is 40-75 years old, with a Body Mass Index (BMI) $\leq 40 \text{ kg/m}^2$.
2. Subject has Kellgren-Lawrence (K-L) severity grade I, II or III in the index knee as determined by X-ray. Contralateral knee: K-L severity grade 0, I or II.
3. Subject has had at least two signs and at least two symptoms of OA disease (based on the European League Against Rheumatism (EULAR) recommendations for diagnosing knee OA in the index knee for at least 6 months despite conservative treatment (weight reduction, physical therapy, pain medications, etc.). The EULAR signs and symptoms are as follows:
 - a. Signs: crepitus, restricted movement and bony enlargement
 - b. Symptoms: persistent knee pain, limited morning stiffness and reduced function

4. Subject must be willing to abstain from other intraarticular (IA) treatments of the knee for the duration of the study.
5. Subject is willing to discontinue all analgesics including NSAIDs, except acetaminophen/paracetamol, at least seven days before the treatment injection and through the completion of the study.
6. Subject is willing to use only acetaminophen/paracetamol (up to a maximum of 4.0 grams per day per the package insert) for the treatment of joint pain for the duration of the study. At least forty eight hours prior to the Baseline Visit and each follow-up visit, the subject is willing to discontinue use of acetaminophen/paracetamol.
7. Subject is willing to maintain a stable dose of oral glucosamine and/or chondroitin sulfate products throughout the study, if taken prior to signing the informed consent form (ICF).
8. Subject is able to understand and comply with the requirements of the study and voluntarily provides consent.

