10.2.12 Medications

Medications that the subject may have been taking prior to enrollment in Cingal 16-02 for conditions unrelated to the treatment of knee osteoarthritis, other than analgesics including NSAIDs, may be continued through to Cingal 17-02 as long as they will not interfere with study assessments. If the subject was taking oral glucosamine and/or chondroitin sulfate products for the treatment of knee osteoarthritis prior to signing the informed consent form for Cingal 16-02, the products may be continued through to Cingal 17-02, but the subject must maintain a stable regimen for the duration of the Cingal 16-02 and the Cingal 17-02 studies.

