12.1.3 Exploratory Endpoints

Any comparisons between groups (Cingal, Monovisc, TH), within groups and / or time points (from baseline through to 39 weeks) not described in the primary or secondary endpoints may be presented

in the exploratory endpoints including:

- EuroQoL (EQ-5D)
- WOMAC Pain Score (100mm VAS)
- OMERACT-OARSI
- Total WOMAC
- WOMAC Stiffness Score
- WOMAC Physical Function Score
- Patient Global Assessment
- Evaluator Global Assessment
- Range of Motion
- Rescue Medication Usage: Difference in analgesic use measured by number of pills taken between visits will be compared between treatment groups descriptively.
- Number of Subjects Considered Treatment Failures: Treatment Failure: A subject who undergoes a procedure or uses a medication (other than the rescue medication) for the treatment of OA in the index knee at any time after the study injection through the 39 week visit.

For the exploratory analyses, the continuous variables will be analyzed via an analysis of variance and contrasts used to assess the prescribed comparisons. For the discrete variables, a Fisher's exact test will be used to assess the desired comparisons.

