4.1.4 Exploratory Endpoints

Any comparisons between groups (Cingal, Monovisc, TH), within groups and / or time points (from baseline through to 39 weeks) not described in the primary or secondary endpoints may be presented in the exploratory endpoints including:

- EuroQoL (EQ-5D)
- WOMAC Pain Score (100mm VAS)
- OMERACT-OARSI
- Total WOMAC
- WOMAC Stiffness Score
- WOMAC Physical Function Score
- Patient Global Assessment
- Evaluator Global Assessment
- Range of Motion
- Rescue Medication Usage: Difference in analgesic use measured by number of pills taken between visits will be compared between treatment groups descriptively.
- Number of Subjects Considered Treatment Failures: Treatment Failure: A subject who undergoes a procedure or uses a medication (other than the rescue medication) for the treatment of OA in the index knee at any time after the study injection through the 12 week visit.

For the exploratory analyses, the continuous variables will be analyzed via an analysis of variance and contrasts used to assess the prescribed comparisons. For the discrete variables, a Fisher's exact test will be used to assess the desired comparisons.

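### The Treatment Failure definition exempts only rescue medication, so read literally it counts permitted, stable glucosamine/chondroitin users as failures, against the endpoint's own name; this affects one exploratory count.

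*Protocol*

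**What the plan says.** **The operative rule.** Under Protocol section 2, an additional procedure makes a subject a treatment failure, and so does being one who "uses a medication (other than the rescue medication) for the treatment of OA in the index knee at any time after the study injection"; the window closes at week 39. Protocol 12.1.3 repeats it with the same window: "A subject who undergoes a procedure or uses a medication (other than the rescue medication) for the treatment of OA in the index knee". SAP 4.1.4 has the same rule, but its window runs "at any time after the study injection through the 12 week visit". Rescue medication is the only exemption in all three places.

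**The permitted products.** The parent study's inclusion criterion 7, reproduced in Protocol 9.1.1, reads "Subject is willing to maintain a stable dose of oral glucosamine and/or chondroitin sulfate products throughout the study", if they were taken before consent. Protocol 10.2.12, headed Medications, begins its permission with "If the subject was taking oral glucosamine and/or chondroitin sulfate products for the treatment of knee osteoarthritis prior to signing" consent to the parent study, and lets such subjects continue through 17-02 on an unchanged regimen. Protocol 10.3 repeats the stable-dose condition. The restricted list in Protocol 10.2.12.1 does not name these products.

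**The endpoint's name.** The synopsis, Protocol 7.3 and SAP 3.3 all list it as "Number of Treatment Failures due to Additional Procedure or Use of Disallowed Medication".

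**The concern.** The definition and the name classify the same subject differently. A subject who took glucosamine for knee OA before consent and kept the dose constant has used a non-rescue product for OA after the injection, and so meets the definition. That subject has used nothing disallowed, and so is not a failure under the name.

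If the literal rule were applied, true failures would be mixed with subjects who followed the protocol exactly. Use that predates randomization should be balanced across arms in expectation. It would therefore add about the same proportion of spurious failures to each arm and pull the comparison towards no difference. If the conflict is left open, the choice between readings falls to the programmer or to a decision made once data are in hand.

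**Working it through.** **Step 1: apply each text to the same subject.** The documents state no failure rate, supplement prevalence or power for this endpoint, so there is no figure of theirs to reproduce. The first check is textual.

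| Subject | Definition (Protocol 2, 12.1.3; SAP 4.1.4) | Endpoint name (synopsis, Protocol 7.3; SAP 3.3) |
|---|---|---|
| Additional procedure for OA in the index knee | Failure | Failure |
| Prohibited analgesic for OA in the index knee | Failure | Failure |
| Rescue medication only | Not a failure | Not a failure |
| Stable glucosamine/chondroitin for knee OA, begun before consent | Failure if read literally | Not a failure |

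The texts disagree in the last row. The word that would settle it, disallowed, is missing from all three statements of the rule, including the two in the analysis sections.

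**Step 2: direction if the literal rule is used.** Let p be the true failure probability in an arm and g the share of permitted users. Assume g is the same in each arm and independent of true failure.

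- Observed rate: p′ = g + (1 − g)p
- Risk difference: p′(TH) − p′(Cingal) = (1 − g) × [p(TH) − p(Cingal)]
- Spurious failures in an arm of size n: n(1 − p)g

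The shrinkage factor (1 − g) holds for any pair of true rates.

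**Step 3: illustrative size.** Inputs from the documents are 256 Cingal and 64 TH (Protocol 12.1), Fisher's exact test for discrete exploratory variables (12.1.3) and a 5% level (12.2). Inputs assumed here are true rates of 10% and 20%, and g of 5%, 15% and 25%. Example at g = 15%: Cingal 0.15 + 0.85 × 0.10 = 23.5%; TH 0.15 + 0.85 × 0.20 = 32.0%. Power comes from exact two-sided Fisher enumeration.

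| g | Cingal | TH | Risk difference (points) | Ratio TH/Cingal | Spurious failures, Cingal / TH | Fisher power |
|---|---|---|---|---|---|---|
| 0 | 10.0% | 20.0% | 10.0 | 2.00 | 0 / 0 | 0.52 |
| 5% | 14.5% | 24.0% | 9.5 | 1.66 | 11.5 / 2.6 | 0.42 |
| 15% | 23.5% | 32.0% | 8.5 | 1.36 | 34.6 / 7.7 | 0.27 |
| 25% | 32.5% | 40.0% | 7.5 | 1.23 | 57.6 / 12.8 | 0.18 |

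**Step 4: other assumed rates.** With 5% versus 15%, power is 0.70 at g = 0 and 0.49, 0.39, 0.24 and 0.16 at g = 5%, 10%, 20% and 30%. With 10% versus 25%, it is 0.82 at g = 0 and 0.71, 0.60, 0.43 and 0.31 at the same values of g. The pattern is the same, but the size depends entirely on the assumptions.

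**The case against.** A reader might infer that the definition makes every glucosamine or chondroitin user a failure, and that the count is therefore inflated. The documents do not support that as a statement of fact, for four reasons.

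- **The name can limit the definition.** Both documents name the endpoint with the disallowed-medication limit. Read together with the permission in 10.2.12, a stable user is not a failure. This stands, and it makes the inflation conditional.
- **Nothing shows which text would be programmed.** Neither document gives a derivation or code for treatment failure. The medication fields in Protocol 10.2.12.3 include indication but no permitted/disallowed flag. That makes the literal derivation easy to write, but does not show that it is planned.
- **Criterion 7 is not itself contradicted.** It governs eligibility and dose stability and says nothing about failure. The conflict lies between the definition and the endpoint's name. Protocol 10.3 also calls the products supplements, so it is arguable whether they are medications at all, although 10.2.12 deals with them under that heading.
- **The stakes are low.** This is one item in a list of exploratory comparisons that may be presented, with no power target and no place in the testing hierarchy. The ratio also looks worse than the absolute effect: at g = 15% it falls from 2.00 to 1.36 while the risk difference moves from 10.0 to 8.5 points. Participation in 17-02 is optional, so 256 and 64 are the most that could contribute at week 39.

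None of this removes the disagreement. The qualifier is missing wherever the rule itself is stated.

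**Conclusion.** The point holds in a limited form. As worded, the operative rule counts compliant users of permitted OA products as failures, while the endpoint's name excludes them. That is an error in a stated rule, and it can be confirmed from the text alone.

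The consequence is conditional. If the rule is applied literally, the count is inflated in every arm and the risk difference shrinks by (1 − g). The documents give neither g nor the failure rates, so the size for this trial is unknown. The fall in power from 0.52 to between 0.42 and 0.18 rests on assumed rates of 10% and 20%, g of 5% to 25%, equal use across arms, independence from true failure, and full arm sizes. It should not be quoted as an expected loss.

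Only one exploratory endpoint is touched; the primary and secondary analyses do not use it. The SAP's 12-week window against the Protocol's 39 weeks is a separate, explicit contradiction in the same definition and needs no interpretation.

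**What to change.** Reconcile the definition with the endpoint name in Protocol section 2, Protocol 12.1.3 and SAP 4.1.4. State that only additional procedures, and medications for OA in the index knee that the protocol does not permit, count as failures, and that glucosamine/chondroitin products continued unchanged under 10.2.12 do not. This alters an analysis definition only; what subjects may take stays the same.

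In the same edit, reconcile the SAP 4.1.4 window with the 39 week visit in Protocol 2 and 12.1.3. If only the exemption were changed, the two documents would still count different failures.

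The cost is one clause in three places and one corrected window. No new data are needed: Protocol 10.2.12.3 already records medication name, dose, frequency, dates and indication, which is enough to identify a permitted product on an unchanged regimen. Make the change before database lock and unblinding, so that no one decides who failed after seeing results.

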3 STUDY SYNOPSIS

Title	Extension Study to Cingal 16-02: Trial Extension to 39 Week Follow Up in the Randomized, Double-Blind, Active Comparator Controlled, Multi-Center Study of a Single Injection Cross-Linked Sodium Hyaluronate Combined with Triamcinolone Hexacetonide (Cingal) to Provide Symptomatic Relief of Osteoarthritis of the Knee
Study Objective	To evaluate the efficacy and safety of a single injection of Cingal for relief of joint pain at 39 week follow up in subjects with Osteoarthritis (OA) of the knee who have not responded to conservative treatment.
Investigational Product	Subjects enrolled in Cingal 17-02 will not receive an injection. For reference only, the investigational product utilized in Cingal 16-02 was: Cingal : A chemically cross-linked sodium hyaluronate supplied as a 4-mL unit dose with a nominal 18 mg of triamcinolone hexacetonide (TH) in a 5-mL glass syringe.
Comparator Product	Subjects enrolled in Cingal 17-02 will not receive an injection. For reference only, the comparator products utilized in Cingal 16-02 were: Triamcinolone Hexacetonide (TH) : 20 mg/ml supplied as 1 mL unit dose in a glass ampoule. Monovisc® : A chemically cross-linked sodium hyaluronate supplied as a 4-mL unit dose in a 5-mL glass syringe.
Mode of Delivery	For reference only, the mode of delivery in Cingal 16-02 was: Cingal, Triamcinolone Hexacetonide, or Monovisc will be injected into the intraarticular (IA) space of the index knee using an 18-21 gauge needle.
Study Design	Multi-center, randomized, double-blind, parallel group, 3-arm, active comparator controlled study
Phase	Phase III
Sample Size	A total of 576 subjects will be enrolled. This equates to 256 subjects injected with Cingal, 256 subjects injected with Monovisc and 64 subjects injected with TH. All subjects who meet enrollment criteria and completed the 26 week follow up in Cingal 16-02 will have the option to participate in the sub-study.
Study Duration	The entire sub-study duration will be an additional 13 weeks. The follow up visit will be scheduled at 39 weeks post treatment.
Inclusion Criteria	
 Only subjects that were enrolled and met the inclusion criteria for the Cingal 16-02 trial and signed the informed consent are eligible for Cingal 17-02 trial. Subject is able to understand and comply with the requirements of Cingal 17-02 and voluntarily provides consent. 
Patients will not be rescreened at enrollment to Cingal 17-02 as these patients were enrolled and met the inclusion / exclusion criteria for the Cingal 16-02 clinical trial.
 
For reference only, the inclusion criteria used in Cingal 16-02 were:
 
 Subject is 40-75 years old, with a Body Mass Index (BMI) $\leq 40 \text{ kg/m}^2$. Subject has Kellgren-Lawrence (K-L) severity grade I, II or III in the index knee as determined by X-ray. Contralateral knee: K-L severity grade 0, I or II. Subject has had at least two signs and at least two symptoms of OA disease (based on the European League Against Rheumatism (EULAR) recommendations for diagnosing knee OA) in the index knee for at least 6 months despite conservative treatment (weight reduction, physical therapy, pain medications, etc.). The EULAR signs and symptoms are as follows: 
 Signs: crepitus, restricted movement and bony enlargement

	
 ○ Symptoms: persistent knee pain, limited morning stiffness and reduced function 
 4. Subject must be willing to abstain from other IA treatments of the knee for the duration of the study. 5. Subject is willing to discontinue all analgesics including NSAIDs, except acetaminophen/paracetamol, at least seven days before the treatment injection and through the completion of the study. 6. Subject is willing to use only acetaminophen/paracetamol (up to a maximum of 4.0 grams per day per the package insert) for the treatment of joint pain for the duration of the study. At least forty eight hours prior to the Baseline Visit and each follow-up visit, the subject is willing to discontinue use of acetaminophen/paracetamol. 7. Subject is willing to maintain a stable dose of oral glucosamine and/or chondroitin sulfate products throughout the study, if taken prior to signing the informed consent form (ICF). 8. Subject is able to understand and comply with the requirements of the study and voluntarily provides consent.
Exclusion Criteria	
Patients will not be rescreened at enrollment to Cingal 17-02 as these patients were enrolled and met the inclusion / exclusion criteria for the Cingal 16-02 clinical trial.
 
Only patients enrolled in the Cingal 16-02 trial will be eligible to participate in Cingal 17-02.
 
For reference only, the exclusion criteria used in Cingal 16-02 were:
 
 1. Subject received an IA injection of Hyaluronic Acid (HA) and/or steroid in either knee within 6 months of signing the informed consent form (ICF). A subject will be excluded if they are planning to receive an HA or steroid injection (other than the study injection) in either knee during the course of this study. 2. Subject had an arthroscopy of either knee within 3 months of signing the ICF. 3. Subject had an open surgical procedure of either knee or hip or any surgery of the spine within 12 months of signing ICF. Subject plans to have knee, hip or spine surgery within the study period. 4. Subject has intra-articular trauma to the index knee. Subject has concurrent multi-system or multi-limb trauma. 5. Subject has evidence or medical history of the following diseases in the index knee: septic arthritis; inflammatory joint disease; history of Reiter's syndrome; gout; chondrocalcinosis associated with recurrent episodes of acute synovitis of the knee consistent with pseudogout; osteochondritis dissecans, Paget disease of the bone; ochronosis; acromegaly; hemochromatosis; primary osteochondromatosis; known history of Wilson disease; heritable disorders or collagen gene mutations. 6. Subject has a history of cartilage repair surgery in the index knee within 3 years of signing the ICF. 7. Subject has a history of ACL repair, reconstruction or injury in the index knee within 3 years of signing the ICF. 8. Subject has X-ray findings of acute fractures, severe bone loss, avascular necrosis, severe bone or joint deformity in the index knee. 9. Subject has significant varus or valgus deformity greater than 10 degrees in either knee. 10. Subject has a clinically apparent tense effusion of the index knee. 11. Subject has knee instability in either knee per the Investigator's assessment. 12. Subject requires consistent use of an assistive device (e.g. wheelchair, walker, etc.) Occasional use of a cane is acceptable. 13. Subject has medical condition(s) which could affect study assessments or may adversely affect the safety and/or success of the study treatment. This includes but is not limited to the following: a. Peripheral neuropathy severe enough to interfere with evaluation of the subject, b. Vascular insufficiency severe enough to

	
interfere with evaluation of the subject, c. Active fibromyalgia, d. Hemiparesis involving either lower extremity, e. Immunocompromised or immunosuppressive disorder or receiving medications to treat immunosuppressive disorders, f. Systemic bleeding disorder(s), g. Current malignancy or treatment within the last 5 years, except for non-melanoma skin cancer, h. Significant psychiatric disorder, i. Active drug and/or alcohol abuse within the past year, j. Uncontrolled diabetes with a screening HbA1c of >7%.
 
14. Subject is taking medications at the time the subjects signs the ICF which could interfere with the treatment procedure, healing and/or assessments. This includes but is not limited to oral or injectable anticoagulant treatments, anti-aggregant platelet treatment, chronic opioid analgesics. Low dose aspirin used for cardiovascular protection is allowed if a stable regimen is maintained for the duration of the study.
 
15. Subject is receiving treatment using electromagnetic stimulation and/or low intensity ultrasound in the index knee at the time of signing the ICF, within 3 months of signing the ICF or plans to receive treatment any time during the study period.
 
16. Subjects who had an oral, intramuscular, intravenous, rectal suppository or topical (excluded in index knee only) corticosteroid within 30 days of signing the ICF are excluded. Topical corticosteroid use at any site other than the index knee is allowed.
 
17. Subject has a pre-treatment contraindication to IA injections or aspiration of the index knee, including cutaneous infection in the injection site area, active IA infection (as suggested by moderate or marked effusion), knee deformity or condition which, in the opinion of the Investigator could jeopardize the sterility or delivery of the IA injection.
 
18. Subjects with a history of hypersensitivity to any of the ingredients in the hyaluronan or previous hypersensitivity to the administration of corticosteroids or an inability to tolerate acetaminophen/paracetamol.
 
19. Subject has any contraindication to the receipt of a corticosteroid.
 
20. Subject is receiving or in litigation for worker's compensation.
 
21. Subject is a woman who is pregnant or breastfeeding at the Screening Visit or a woman of child bearing potential who refuses to use effective contraception during the course of the study.
 
22. Subject was involved in any other research study involving an investigational product, or a new application of an approved product, within 60 days of signing the ICF.
 
Baseline Inclusion Criteria
 
 1. Subject has a Western Ontario and McMaster Universities Osteoarthritis Index (WOMAC) pain-sub-score ≥ 40 mm and ≤ 90 mm in the affected knee and ≤ 30 mm in the contralateral knee on a 100 mm Visual Analog Scale (VAS) scale. 
Baseline Exclusion Criteria
 
 1. Subject has a decrease of ≥ 20 mm in the WOMAC pain-sub-score (average of 5 pain scales) from Screening to Baseline in the index knee on a 100 mm Visual Analog Scale (VAS) scale. 2. Subject has a synovial fluid aspirate volume > 20 mL in the index knee. 3. Subject has a contraindication to continue with the study treatment injection based on the visual appearance of the synovial fluid aspirate unless the fluid is examined microscopically prior to injection with no clinically significant findings (e.g. bacteria, crystals or blood). 4. Subject has range of motion of less than 100° flexion in either knee.
--	--

Criteria for Evaluation	
Efficacy:
 
Primary Endpoint:
 
 The responder rate as identified by the Outcomes Measures for Rheumatic Arthritis Clinical Trials-Osteoarthritis Research Society International (OMERACT-OARSI) responder index at 39 weeks post treatment comparing the Cingal group to the TH group. 
Secondary Endpoints:
 
 The change from baseline in knee pain as measured by the WOMAC Pain Score (100 mm VAS) at 39 weeks post treatment comparing the Cingal group to the TH group. The change from baseline in WOMAC Physical Function score at 39 weeks post treatment comparing the Cingal group to the TH group. The change from baseline in WOMAC Stiffness score at 39 weeks post treatment comparing the Cingal group to the TH group. The change from baseline in Total WOMAC score at 39 weeks post treatment comparing the Cingal group to the TH group. The change from baseline in the Patient Global Assessment 39 weeks post treatment in the Cingal group compared to the TH group. The change from baseline in the Evaluator Global Assessment at 39 weeks post treatment in the Cingal group compared to the TH group. The usage of rescue medication through 39 weeks post treatment in the Cingal group compared to the TH group. 
Exploratory Endpoints:
 
Any comparisons between groups (Cingal, Monovisc, TH), within groups and / or time points (from baseline through to 39 weeks) not described in the primary or secondary endpoints may be presented in the exploratory endpoints including:
 
 ○ EuroQol (EQ-5D) ○ WOMAC Pain Score (100mm VAS) ○ OMERACT-OARSI ○ Total WOMAC ○ WOMAC Stiffness Score ○ WOMAC Physical Function ○ Patient Global Assessment ○ Evaluator Global Assessment ○ Range of Motion ○ Rescue Medication Usage ○ Number of Treatment Failures due to Additional Procedure or Use of Disallowed Medication 
Safety:
 
The incidence, timing, severity, and relationship to treatment of all Adverse Events (AE) will be collected and coded using Medical Dictionary for Regulatory Activities (MedDRA). Local injection site and non-local events will be recorded separately.

Statistical Analysis	
The primary analysis on the endpoints will be performed on the ITT (Intent to Treat) populations. All Primary and Secondary endpoints will be analyzed using the ITT population.
 
A secondary analysis will be conducted on the Per Protocol (PP) population. Since the primary endpoint is at 39 weeks, this is all subjects who complete the 39 week visit and who are not major violators of the protocol. For all other visits, this is defined as the subjects who complete those visits according to the protocol.
 
All safety analyses will be conducted on all subjects who undergo treatment in any group.

Sites	Up to 40 clinical sites within Europe may participate.
Sponsor	Anika Therapeutics, Inc. [name] Bedford, MA 01730, United States of America Phone: + 1 [contact] Fax: + 1 [contact]

